Initial assessment findings will be reviewed and those participants who still appear to be eligible for study participation will be invited to come to the research office for blood work, urine toxicology and a medical history and vital signs. A urine toxicology screen is obtained to check for recent drug use. Women will complete urine pregnancy testing. Subjects will undergo a medical history, and standard laboratory tests (complete blood count, comprehensive metabolic panel) and a 12-lead ECG. In rare cases, MIFE can cause low blood potassium and cardiac changes. We will exclude individuals with potassium levels below the normal range or who have any clinically significant abnormality on the ECG. The ECG and medical records will be reviewed by the study physician ([name]). Psychiatric and behavioral assessments will be reviewed by [name], Co-PI and a licensed psychologist. We are eliminating all sections of the brief physical examination (PE) from the protocol except vital signs to enhance safety for staff nurse and physician. We have determined that the PE findings have never contributed to ruling out participation by participant. The detailed medical history will be obtained. We expect to assess 3 people for each eligible participant; thus the total assessed sample will be 450 subjects. Because of the risk of confounding by smoking rates and severity among AUD subjects, we will recruit an equal number of HC smokers, matched on Fagerstrom scores.

General CRU procedures:

For AUD subjects, this study will be completed as a 7 day (6 night) inpatient protocol on the Bayview Clinical Research Units (CRU). We will conform with all COVID-related safety procedures implemented by the CRU.

On Day 1 prior to completion of any study procedures, subjects will undergo a urine toxicology for recent alcohol and drug use; a drug positive other than marijuana will result in rescheduling study procedures. Female subjects will complete a urine pregnancy test; positive subjects will be excluded from further study procedures. Vital signs (BP and HR) and laboratory tests (CBC and CMP) will be obtained. Updated assessment measures will include an interim timeline follow-back of alcohol use.

During the Bayview CRU stay, participants will be allowed to smoke; subjects will be smoking abstinent for 2 hours prior to study procedures. They will have the option to receive a transdermal patch (21 mg) while off the CRU to complete study procedures.

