Because MIFE is occasionally associated with hypokalemia, serum potassium level is obtained before study procedure at 7:00 am on day 1 and at the 1 week follow-up. Potassium replacement will be addressed as needed. MIFE levels will also be tested at day 4.

On day 4, outpatient HC participants will return to the office in the morning and complete the study procedures.

Alcohol Withdrawal Management:

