Since MIFE has potent antiprogestational effects, women participants will undergo a urine pregnancy test at the time of the initial alcohol sensitivity and prior to the first MIFE dose. On day 1, participants will be dosed after the fMRI session under nursing observation. On all subsequent days, inpatient participants will be dosed once daily at 9 am under nursing observation and HC outpatient participants will be given take home medication and asked to take the medication under nursing observation via video teleconference. Blood draws for MIFE trough and peak plasma level determinations will be drawn at 15 minutes before dosing and 90 minutes after dosing, respectively. MIFE blood draws will be completed for outpatient HC participants on day 4 only. Subjects can discontinue taking study medication at any time, ending study participation. Discontinued subjects will be asked to complete post-discharge follow up.

fMRI scans for functional connectivity and alcohol cue activation on Days 1 and 4: Both AUD and HC participants undergo fMRI sessions. On day 1, all subjects report to the IPSAR office at 9 am, complete interim assessment procedures, urine drug and pregnancy screens and receive a calorie-controlled breakfast. AUD and HC smokers with tobacco use disorder (TUD) will receive a nicotine patch (21mg). At 10 am on day 1 only, AUD subjects will receive an alcohol drink in a standardized calorie-free mixer targeting a blood alcohol level of 80mg% based on gender and BMI. We have included this drink for several reasons. Most importantly, we want to standardize time from last drink to start of scanning across AUD subjects, since subjects will come for admission with varying abstinence durations. Secondly, we want to minimize the impact of both alcohol intoxication and withdrawal on this initial scan, and so have attempted to time the scan to begin when BAL is at or near 0mg%. Finally, we anticipate that this pre-scan drink will act as a primer for the alcohol cuing procedure employed in the study. At 1 pm, all subjects undergo rs-FC and CA fMRI procedures.

fMRI Scanning procedures: All studies will be conducted at 3T in the F.M.Kirby Research Center for Functional Brain Imaging. We will follow all COVID-related safety procedures implemented by the Kirby Research Center. We will counter-balance for handedness and always use the right hand for responses.

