As shown in Figure 1, cumulative alcohol dosing procedures generate highly reproducible BALs and subjective effects, with little between-subject variability. Subjective effects track BAL across the ascending and descending limb of the curve. Using this procedure, we have shown that the GABRA2 gene influenced alcohol subjective and physiological effects (Uhart et al., 2013). To date, we have completed this procedure over 150 subjects.

[figure not shown]

Figure 1. Time course of BAL and self-rated effects on the VAS and SHAS. Arrows indicate times of placebo

(P) and each alcohol drink (A1, A2, A3) consumed.

Discharge and Follow-up:

AUD subjects are discharged on day 7 following cognitive assessment and participation in a brief motivational intervention for alcohol use; information on treatment availability will be provided prior to discharge from the CRU. Under the supervision of [name], the intervention is delivered by Master's-level staff following procedures outlined in NIAAA Clinician Guide to Brief Intervention.

All female participants are advised to use nonhormonal birth control (e.g., condoms) for the duration of a one month period following discharge. All male participants will also be advised to use condoms for the duration of the follow-up visits and for at least 5 half-lives of the drug plus 90-days after the last dose of mifepristone. All subjects will be given a supply of condoms.

AUD subjects return weekly for 2 follow-up visits. HC subjects return one week post-second fMRI for a follow-up visit. As described above, MIFE is a long acting compound; plasma levels will likely remain elevated throughout the first two weeks post-discharge at the time of the follow-up visits. At each follow-up visit, participants provide self-reported alcohol use using TLFB procedures for the period since they were last seen, complete self-report measures of alcohol craving (as listed under the inpatient stay), medication side effects (SAFTEE) and adverse events. In addition, we will obtain a blood spot for PEth determination as a biomarker of recent drinking intensity. We also will get a blood sample for MIFE level and, at week 1 follow-up, a sample will be obtained to test for potassium level. Subjects will be reminded of the importance of use of nonhormonal birth control and/or condoms and will be provided with condoms.

b. Study duration and number of study visits required of research participants.

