Each subject will participate in an initial assessment, and a possible second assessment visit for completion of medical history, vital signs and laboratory tests. AUD participants will be admitted to the CRU for 6 nights. HC participants, who participate in the study on an outpatient basis, will continue MIFE dosing and salivary sample collection at home. For AUD participants, there are two follow-up visits at 1 and 2 weeks following CRU discharge. For HC participants, there is one follow-up visit at 1 week following the second fMRI. It is anticipated that subjects will complete all study procedures within a 6 month period.

c. Blinding, including justification for blinding or not blinding the trial, if applicable.

Staff and subjects will be blind to the alcohol and MIFE doses administered during this study to reduce expectancy effects.

d. Justification of why participants will not receive routine care or will have current therapy stopped.

Subjects are not seeking treatment for their AUD; they will not currently be engaged in therapy.

e. Justification for inclusion of a placebo or non-treatment group.

A placebo MIFE dose is included for comparison with the active drug effects and to control for expectancy effects.

f. Definition of treatment failure or participant removal criteria.

A participant will be removed from the study if s/he experiences a moderate or severe adverse event, is noncompliant with study or CRU rules, or if it is determined by the study physician to be unsafe to continue.

g. Description of what happens to participants receiving therapy when study ends or if a participant's participation in the study ends prematurely.

MIFE dosing is discontinued at the time of discharge from the study.

5. Inclusion/Exclusion Criteria

Healthy, non-treatment seeking, 21-60 years old, male and female subjects will be recruited through the media. Recruitment uses a mix of newspaper, radio, and on-line advertisements. Based on the 2011 census, the Baltimore metropolitan area is mostly Caucasian (61%) or African-American (30%); the remaining 9% is Asian (4%) and persons reporting two or more races (5%); 8.8% of the population report Hispanic ethnicity.

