Subjects will be carefully screened and fully informed of study procedures and risks prior to participation in any study procedures. This study involves several procedures, each of which entails some risk of discomfort or side-effects. It also employs several drugs, each of which entails some risk. These risks are discussed by procedure and medication. Participants will receive a thorough description of all potential risks in the consent form.

Assessment procedures: The major disadvantage is the time taken to complete study instruments and questionnaires. Our experience with these evaluations indicates they are acceptable to participants. This study involves questions about dangerous or illegal behavior, psychiatric history, a medical history, and laboratory tests. There is a small risk that participants will become upset during the assessment interview. There also is a risk of breach of confidentiality if the responses were to be disclosed.

Blood draws and urine collection: We will collect blood for health assessment and medication levels. Blood chemistries and urinalysis are performed at baseline, at the time of admission to the CRU (or day 1 for HC participants completing the study on an outpatient basis), and on protocol days 4 – 6. Urinalysis for drug toxicology assessment is performed to identify illicit drug use. A blood spot for PEth testing is obtained for detection of recent heavy drinking; PEth blood spot is collected at assessment and each follow-up visit. Urine pregnancy tests are completed in female subjects at screening and on day 1. A urine pregnancy test is obtained prior to the initial MIFE dose. Blood draw procedures involve minimal risks such a slight risk of discomfort at the intravenous site. A small amount of bleeding under the skin will produce a bruise in about 5% of cases. The risk of temporary clotting of the vein is about 1%. The risk of infection or significant blood loss is less than 1 in 1000. In rare cases, fainting could occur.

Alcohol Withdrawal: Applicants with a history of prior inpatient medicated withdrawal, alcohol withdrawal-related seizures, or other serious alcohol withdrawal symptoms will be excluded from participation. Eligible participants will undergo monitored alcohol abstinence and medically supervised alcohol withdrawal on the CRU.

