- Subjects with potassium levels below the normal range at screening will be excluded. We will also monitor potassium on days 1 and 7 (AUD participants only), and at the 1 week follow-up. Potassium will be administered if clinically needed.
- Based on data from studies and clinical trials, which encompass over 1500 subjects and patients treated for one to two weeks with MIFE doses ranging from 300 mg/day to 1800 mg/day, the risk for development of adrenal insufficiency in persons without Cushing Syndrome is low. Specifically, in studies of psychotic depression and in volunteers with antipsychotic drug induced weight gain as well as healthy volunteers and subjects with hepatic and renal impairment who participated in PK, PD, and DDI studies, there were no AEs of adrenal insufficiency reported (Personal Communication, Corcept Therapeutics). Still, in the current study, subjects will be monitored for the development of the signs and symptoms of adrenal insufficiency (weakness, nausea, increased fatigue, hypotension) during the CRU stay and during outpatient visits. Once on the CRU and following MIFE administration, we monitor for hypoadrenalinism by measuring blood pressure and heart rate along with all vital signs q6 hours. For inpatient participants, we also will be asking questions q6 hours regarding emergence of symptoms of hypoadrenalinism, including the development of fatigue, nausea, vomiting, abdominal pain, loss of appetite, light headedness, arthralgias, and myalgias. Outpatient participants will be asked these questions once daily either in person or by phone. If an AUD subject on the CRU is thought to be developing hypoadrenalinism, we will discontinue the MIFE, support blood pressure with intravenous fluids and infuse 8mg of dexamethasone intravenously. Outpatient healthy control participants will be provided with oral dexamethasone 8 mg to take home. They will be given an instruction sheet (see supplemental study documents) that advises them of the symptoms of adrenal insufficiency and advises them to call [name] if these symptoms start to develop. This dose is more than adequate to reverse the glucocorticoid receptor blockade. The proposed single dose of dexamethasone is routinely used in the determining the etiology of Cushing Syndrome. In patients with impaired glucose tolerance or frank diabetes mellitus, this dose of dexamethasone can transiently increase blood sugar; however, in our study, participants with impaired glucose tolerance are excluded. Dexamethasone will only be used in the unlikely event of adrenal crisis in which we do not anticipate any negative side-effects from the treatment.

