Participants will be paid \$75 for the initial in-person assessment procedures. If all eligibility assessment procedures are not completed during the first assessment visit, we pay participants an additional \$25 to come in a second time to complete procedures.

Subjects who are eligible to continue in the study will be paid for completed procedures and their time and effort in the study. AUD Subjects receive \$15/day as basic CRU earnings and an additional \$10 per day for compliance with CRU and study procedures.

Payments for AUD study completers

Assessment \$75

CRU stay – 7 days X \$25/day (\$15/ day + \$10/day for following protocol rules) = \$175

Alcohol self-administration and sensitivity sessions = \$75/session X 2 = \$150

fMRI = \$100/scan X 2 = \$200

Follow-up visits X 2 = \$100

Bonus - \$200

Subject payment expense: \$900

Payments for outpatient HC study completers

Assessment \$75

Medication/questionnaire compliance = 4 days X \$10/day = \$40

Blood draw on day 4 = \$10

fMRI = \$100/scan X 2 = \$200

Follow-up visit = \$50

Bonus - \$100

Subject payment expense: \$475

Subjects are paid for the eligibility visit in cash after completing the assessment. If the subject is eligible for a bonus payment, it will be dispensed in cash on the day of discharge. Subjects will receive a check for the remaining amount of money that was earned during the rest of the study.

If the Investigator ends the subject's participation because s/he broke study or unit rules or the subject drops out of the study, s/he will be paid only the amount earned to date for completed procedures and the CRU stay. If the participant leaves during the CRU stay, s/he will not be paid any money until the scheduled discharge day, and will forfeit future possible earnings and bonus payments.

11. Costs

a. Detail costs of study procedure(s) or drug (s) or substance(s) to participants and identify who will pay for them.

Costs for all procedures and drugs will be covered by the study.

REFERENCES

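### No potassium test is named for healthy controls while they are on drug, and the general line on day 4–6 blood chemistries does not clearly supply one

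*Combined protocol and SAP*

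**What the plan says.** The statements that name potassium agree with one another for HC.

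- **Screening** (Section 4a, Assessment): the work-up includes "standard laboratory tests (complete blood count, comprehensive metabolic panel) and a 12-lead ECG", and a potassium level below normal is exclusionary. Sections 5 and 8a repeat the exclusion.
- **HC procedures** (Section 4a, Outpatient procedures for HC): "serum potassium level is obtained before study procedure at 7:00 am on day 1 and at the 1 week follow-up". Replacement is promised if needed. The only assay listed there for day 4 is the mifepristone level.
- **Risk minimization** (Section 8b, Mifepristone administration): "We will also monitor potassium on days 1 and 7 (AUD participants only), and at the 1 week follow-up". The bracket most naturally attaches to day 7.
- **Follow-up** (Section 4a, Discharge and Follow-up): "at week 1 follow-up, a sample will be obtained to test for potassium level". Section 4b fixes the visit: "For HC participants, there is one follow-up visit at 1 week following the second fMRI". Table 1 shows it as day 11.

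One further sentence bears on the point. Section 8a, Blood draws and urine collection, lists blood chemistries at baseline, at admission ("or day 1 for HC participants completing the study on an outpatient basis), and on protocol days 4 – 6". It does not mention potassium and does not say which group days 4 to 6 concern.

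HC blood is in any case taken on day 4. Section 4a, MIFE Administration, states: "MIFE blood draws will be completed for outpatient HC participants on day 4 only". Section 10 pays HC for it under "Blood draw on day 4".

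**The concern.** The study is presented as a source of safety information. Adverse events are a primary outcome, and Aim 5 promises close monitoring of side effects in both groups. For a laboratory risk that the protocol names, one would expect at least one value taken while the drug is being given. AUD subjects have one in effect, on day 7. The HC procedures text gives HC none.

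Two things are at stake. Replacement as needed presupposes a result, and without one only symptoms could prompt it before day 11. The study would also lose on-drug potassium data in the group where they are easiest to interpret, since HC receive neither the study alcohol doses nor the intravenous fluids given to AUD subjects on admission.

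**Working it through.** The plan states no figure on this point, so there is nothing to reproduce. The check sets the schedules side by side and adds simple arithmetic.

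**Inputs**
- HC doses: days 1 to 4 (Table 1). The day 1 dose follows the scan, so the day 1 potassium sample is pre-dose (Section 4a, MIFE Administration).
- HC follow-up: day 11 (Table 1).
- AUD doses: days 1 to 6, at 9 am from day 2. AUD potassium: days 1 and 7, and the 1-week follow-up.
- Allocation: 2:1 active to placebo, with 75 HC planned.
- Half-life: 40 h after a single dose and 84.6 h after multiple doses (Section 4a, MIFE Administration); 18 h in Section 8a.

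**Timing**
- Gap between named HC tests after screening: 11 − 1 = 10 days, which spans all four doses.
- Time from last HC dose to the second of these tests: 11 − 4 = 7 days = 168 h.
- Time from last AUD dose to the day 7 test: about 24 h, assuming a morning sample.
- HC on active drug: 75 × 2/3 = 50, assuming the ratio applies within HC.

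**Is day 11 an on-drug sample?** The fraction of parent drug left after t hours is 0.5^(t / half-life), taking simple first-order elimination:

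| Half-life | HC at day 11 (168 h) | AUD at day 7 (24 h) |
|---|---|---|
| 84.6 h | 0.252 | 0.821 |
| 40 h | 0.054 | 0.660 |
| 18 h | 0.0016 | 0.397 |

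On every half-life in the protocol, the AUD day 7 sample is much closer to treatment than the HC day 11 sample. The table shows timing only. It ignores active metabolites, and nothing in the documents links plasma level to a fall in potassium.

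**Does the Section 8a sentence fill the gap?** There are two readings:
- Days 4 to 6 include HC on day 4, and chemistries include potassium. HC then have one on-drug value, and the longest gap falls to 11 − 4 = 7 days.
- Days 4 to 6 describe AUD subjects only. The 10-day gap stands.

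HC have no visit on days 5 or 6, so the range as written cannot apply to them in full. That leaves day 4 open. Table 1 shows HC blood work only before admission and on day 1, but it also omits the day 4 mifepristone draw, so its silence carries little weight.

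**The case against.** The strongest reply is that Section 8a already provides the test. Its sentence refers to HC expressly, does not confine days 4 to 6 to AUD subjects, and HC are on site with blood drawn on day 4. Nor does absence from the procedures text count for much, since that text names no chemistry panel for AUD subjects on days 4 to 6 either. This part of the reply stands. A reader might infer that HC have no chemistry at all during dosing, and the documents do not support that.

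A reader might also infer that the sections contradict one another. They do not. Neither the HC procedures text nor Section 8b says that potassium is tested only at the listed times. The sections differ in completeness.

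A third tempting inference is that HC are exposed to a material hazard. Section 8a reports that hypokalemia has not been seen outside Cushing patients, and low potassium is exclusionary at screening and on day 1. HC also have structured side-effect interviews by video on days 2 and 3, daily questions on adrenal symptoms that overlap with those of low potassium, and instructions to call the study doctor. Day 11 is not drug-free either: metabolites are active, and the follow-up text expects levels to stay elevated.

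What remains is narrow. Symptom questions do not replace a laboratory value, and a general sentence in the risk section is a weak instruction to staff who work from the procedures section.

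**Conclusion.** The point holds as a low-severity improvement. The potassium-specific text gives HC tests at screening, before dosing on day 1 and on day 11, with no named on-drug test, while AUD subjects have one about 24 h after their last dose. If staff follow the HC procedures text, about 50 HC on active drug would have no on-drug potassium value. That consequence is conditional: it rests on the 2:1 ratio holding within HC and on the Section 8a chemistries either not covering HC on day 4 or not including potassium. If they do cover both, only the wording needs attention. On either reading the schedule should be stated once, clearly. The AUD schedule needs no added test.

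**What to change.** State in Section 4a (Outpatient procedures for HC) and Section 8b (Mifepristone administration) that serum potassium is measured in HC from the day 4 blood draw, preferably the pre-dose sample. Keep the day 1 and 1-week tests. In Section 8a, say which group the day 4 to 6 chemistries apply to and whether they include potassium, and add the HC day 4 draw to Table 1. While that text is open, reconcile the 7:00 am potassium sample with the 9 am arrival given for all subjects on day 1.

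The cost is one assay, possibly one extra tube, for each of about 75 HC. No visit or needle stick is added, because the draw is already planned and paid for. One limit should be accepted: day 4 is the last HC dosing day, so the result may arrive after the final dose. Its value lies in detection, replacement in the following week and on-drug safety data, not in dose adjustment.

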AUD subjects will complete medically supervised alcohol detoxification as in our earlier studies (McCaul, [name], Eissenberg et al., 2000; McCaul et al., 2001; Bencherif et al., 2004; Weerts et al., 2008; Weerts et al., 2011; [name] et al., 2013; Weerts et al., 2013). Participants will be required to wear a mask before nurse, staff or housekeeping enter the room. All AUD subjects will receive intravenous D5W NS over the first 12 hours following admission. The Clinical Institute Withdrawal Assessment - Alcohol Revised (CIWA-Ar) (Sullivan et al., 1989), which includes 10-items (nausea/vomiting, tremor, paroxysmal sweats, anxiety, agitation, tactile disturbances, auditory disturbances and visual disturbances), will be completed by CRU nurses every 4 hours while the participant is awake. This well-validated clinical tool will assess alcohol withdrawal symptom severity, and is the gold standard to guide benzodiazepine (BZ) administration during symptom-driven withdrawal management (Saitz et al., 1994). We have successfully studied alcohol withdrawal in our prior research. Scores on the CIWA-Ar are sufficiently elevated that we are able to see reductions in withdrawal severity as a result of research pharmacological intervention. If the CIWA score is ≥ 12 the subject is given intravenous diazepam (5mg) or lorazepam (1mg). The CIWA score is repeated 1 hour after the first diazepam dose. If the score remains ≥ 10 then a second intravenous diazepam dose (5mg) or lorazepam dose (1mg) is given. This procedure is repeated one more time and if the CIWA-Ar score remains ≥ 10 then the participant is transferred to the Bayview ED and terminated from the protocol. Based on our previous study, we anticipate that few subjects will require BZ treatment since we exclude subjects who report a history of withdrawal complications. If systolic blood pressure increases above 180 and/or diastolic blood pressure increases above 105, we may administer atenolol 25 mg po and then titrate as needed. Subjects will be removed from the protocol for seizures, hallucinations, or disorientation or following three doses of diazepam or lorazepam. At that point in time, the physician on call will be contacted. The subject will be transported to the Johns Hopkins Bayview Emergency Department for care. The subject is now terminated from the study.

MIFE Administration:

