Medically supervised and alcohol withdrawal and monitored abstinence: Subjects will be closely monitored by nursing and physician staff for alcohol withdrawal signs and symptoms. All AUD subjects will receive iv administration of 1 liter of normal saline with vitamins over the first 12 hours following admission. On days 1 – 4, the Clinical Institute Withdrawal Assessment - Alcohol Revised (CIWA-Ar), which includes 10-items (nausea/vomiting, tremor, paroxysmal sweats, anxiety, agitation, tactile disturbances, auditory disturbances and visual disturbances), will be completed by CRU nurses every 4 hours while the participant is awake. This well-validated clinical tool will assess alcohol withdrawal symptom severity and is the gold standard to guide benzodiazepine (BZ) administration during symptom-driven withdrawal management (Saitz et al., 1994). If the CIWA score is ≥ 12 the subject is given diazepam (5mg). The CIWA score is repeated 1 hour after each dose. If the score remains ≥ 10 then another diazepam dose (5mg) is given up to a maximum of three doses. Based on our previous study, we anticipate that few subjects will require BZ treatment since we exclude subjects who report a history of withdrawal complications. If systolic blood pressure increases above 180 and/or diastolic blood pressure increases above 105, we may administer atenolol. The most common symptoms of atenolol include dizziness, lightheadedness, tiredness, drowsiness, depression, nausea and diarrhea. Less common but more serious side-effects include: shortness of breath, and swelling of the hands, feet, ankles or lower legs. Subjects who experience seizure activity or delirium tremens will be discontinued from the study; also subjects will be discontinued on recommendation by the study physician. To date we have successfully withdrawn over 98% of our alcohol-dependent subjects without medications requiring protocol termination. Exclusion of subjects with a history of alcohol withdrawal complications, and/or high CIWA scores at assessment is a successful strategy to help ensure subject safety. In the event of a severe reaction or medical emergency, the participant will be transported to near-by emergency services.

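### The alcohol-withdrawal instructions disagree on removal after three rescue doses, on the infusion, and on the days CIWA-Ar is scored

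*Combined protocol and SAP*

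**What the plan says.** **Removal.** Section 4a (Alcohol Withdrawal Management) starts rescue at a CIWA-Ar score of 12 or more and repeats it while the score is 10 or more. After the last repeat, "if the CIWA-Ar score remains ≥ 10 then the participant is transferred to the Bayview ED and terminated from the protocol". A few sentences later it states: "Subjects will be removed from the protocol for seizures, hallucinations, or disorientation or following three doses of diazepam or lorazepam". Section 8b, in its paragraph on supervised withdrawal, says: "If the score remains ≥ 10 then another diazepam dose (5mg) is given up to a maximum of three doses". Its reasons for stopping are given separately: "Subjects who experience seizure activity or delirium tremens will be discontinued from the study", or a recommendation by the study physician.

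**Infusion.** Section 4a: "All AUD subjects will receive intravenous D5W NS over the first 12 hours following admission". Section 8b, also for all AUD subjects after admission: "iv administration of 1 liter of normal saline with vitamins over the first 12 hours".

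**Monitoring days.** Section 8b places the four-hourly CIWA-Ar on days 1-4. Section 4a gives the same four-hourly schedule with no day limit. Table 1 shows alcohol withdrawal monitoring on days 2-6. The Study Overview describes monitoring over the three days that follow day 1.

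**Use in the analysis.** CIWA-Ar is a secondary outcome in Section 7b and one of the main Aim 2 outcomes in Section 7c. The Aim 2 text compares the arms by t-test or a non-parametric equivalent, with ANCOVA. It does not say which days, or which summary of the repeated scores, enter the test.

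**The concern.** These are bedside instructions, and in places two of them cannot both be followed. If staff act on different sentences, two subjects with the same course could be handled differently: one stays for the later procedures and the other is sent to the emergency department and leaves the study. The infusion conflict reaches every AUD subject on admission.

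The scoring days matter for a separate, statistical reason. Subjects can drink again after the day 5 motivated-responding session and are given alcohol in the day 6 sensitivity session. Aim 2 concerns early abstinence. A CIWA-Ar summary that stops at day 4 and one that runs to day 6 therefore measure different things, and the analysis plan does not choose between them.

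**Working it through.** The plan states no figure to reproduce here. The check sets the statements side by side and then bounds the effect on numbers.

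**1. Removal.** I read the Section 4a cycle as ending after a third dose, which agrees with the three-dose count used elsewhere in both sections.

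| Course after a third dose | 4a, score sentence | 4a, dose-count sentence | 8b |
|---|---|---|---|
| Score below 10 | stays | removed | no removal tied to the count |
| Score still 10 or more | emergency department, terminated | removed | no listed trigger except physician recommendation |

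The direct contradiction is the first row, and it lies inside one paragraph of Section 4a. It is not only a matter of which section staff consult.

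**2. Infusion.** Same population and same first 12 hours, but different descriptions. Section 4a gives no volume and mentions no vitamins; Section 8b gives both and names a different fluid.

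**3. Days covered.**

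| Source | Day 1 | Days 2-4 | Days 5-6 |
|---|---|---|---|
| 8b, CIWA-Ar | yes | yes | no |
| 4a, CIWA-Ar | no limit stated | no limit stated | no limit stated |
| Table 1, withdrawal monitoring | not in that row | yes | yes |
| Study Overview, monitoring | no | yes | no |

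Only days 2-4 are common to all four. If each day carried equal weight in a summary score, days 5-6 would supply 2/5 = 40% of it under the Table 1 period and none under Section 8b. Day 1 would supply 1/4 = 25% under Section 8b and none under Table 1.

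**4. Rescue wording (lesser point).** The thresholds of 12 and 10, the 5 mg diazepam dose and the count of three agree. Section 4a specifies the intravenous route, allows lorazepam 1 mg as an alternative, and mentions re-scoring one hour after the first dose. Section 8b names diazepam only, gives no route, and re-scores after each dose.

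**5. Bound on numbers lost.** Inputs: 75 AUD subjects (Study Overview); 2:1 allocation (Section 4a, MIFE Administration), so 50 and 25; over 98% withdrawn in the past without medication requiring termination (Section 8b); over 90% completing (Section 5). The last two give upper rates of 2% and 10%. The 10% is loss from all causes, so it is a generous ceiling. The 5% row is my assumption.

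Expected loss = 75 × rate. The detectable standardized difference is for a two-sided t-test at alpha 0.05 with 80% power. As a check, the normal approximation with no loss is (1.960 + 0.842) × √(1/50 + 1/25) = 0.686; the t-based value is 0.695.

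| Loss rate | Expected lost of 75 | Detectable difference (SD units) |
|---|---|---|
| 0% | 0 | 0.695 |
| 2% | 1.5 | 0.703 |
| 5% | 3.75 | 0.714 |
| 10% | 7.5 | 0.734 |

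At 2% the chance of at least one such loss is 1 − 0.98^75 = 78%. So a termination decision is likely to arise at least once, though few subjects would be involved. The documents give no rate for the disputed case itself (three doses, then below 10).

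**The case against.** The best defence is that Section 8b is a risk summary, not the operating procedure. It sets a dose ceiling, never says that subjects who reach it stay in, does not call its list of reasons exhaustive, and leaves room for the physician. Its own reference to medication requiring termination suggests that it expects such removals. That stands: a reader might infer that Section 8b positively authorizes keeping a subject after three doses, but it is only silent. Likewise, the dose-count sentence in Section 4a may be shorthand for the score-based one. That is possible, but as written the two give opposite results for the subject who settles, and a nurse cannot know which was meant.

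On monitoring, Table 1 does not name CIWA-Ar, day 1 has its own row, and the Overview fits Section 8b fairly well. This weakens the clash with Table 1. It does not supply a stated window for the endpoint, because Section 4a has no limit and Section 7c is silent.

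The differences on rescue drug and route are mostly omissions in Section 8b and should not be presented as a safety conflict for all 75 subjects. Only the infusion and the scoring days reach everyone.

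A reader might also infer that the inconsistency biases the arm comparison in one direction by removing more subjects from the arm with worse withdrawal. The documents do not support that. Removal linked to severity would occur under any single termination rule, staff are blinded (Section 4c), and any direction depends on whether the drug works. Nor does removal always cost the second scan: that is lost only if it happens before the day 4 session.

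**Conclusion.** The point holds as an internal inconsistency in three places: removal after a third dose, the infusion, and the CIWA-Ar days. The first concerns the few subjects expected to need benzodiazepines. The other two concern all 75 AUD subjects.

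For the analysis, the consequence that counts is the undefined CIWA-Ar window, with up to 40% of an equally weighted daily summary at issue under the Table 1 period. Retention is a minor matter. On the protocol's historical figure about 1 to 2 of 75 would be lost, and the detectable difference moves from 0.695 to 0.703. This assumes that past experience carries over and that the 2% is a fair ceiling for terminations of this kind. Even at the all-cause 10% the detectable difference reaches only 0.734. No bias in either direction has been shown.

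It should be corrected because the text cannot be followed consistently as written. It does not by itself threaten the trial's conclusions.

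**What to change.** Reconcile the Study Overview and Table 1, the Alcohol Withdrawal Management text in Section 4a, and the withdrawal paragraph in Section 8b, so that the rescue, termination, infusion and CIWA-Ar schedule statements agree. Check the result against the removal criteria in Sections 4f and 7d, so that there is one consistent account of when a subject leaves the study. Which drugs, routes, fluids, thresholds and removal rules apply is for the investigators to decide; this point proposes none.

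Then add to the Aim 2 analysis in Section 7c the CIWA-Ar days that result and the summary of those scores that enters the test, settled before unblinding.

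The cost is a wording amendment and a short addition to the analysis text. No change to the sample size is needed.
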